## Table 2: Complications

Complication	Mild	Moderate	Severe
Bleeding:	Transfuse	Embolisation (IR)	Return to theatre
Infection - chest:	Antibiotic	Oxygen support	Ventilation / intensive
			care
Infection - urine:	First line antibiotic	Second line antibiotic	Pyelonephritis
Infection - Intra-	Antibiotic	Interventional radiology	Laparotomy
abdominal:			
Wound - infection at	Antibiotic	Interventional radiology	Laparotomy
stoma site:			
Wound - infection at	Antibiotic	Interventional radiology	Laparotomy
	Superficial (skin)	Doop (fascia)	Poturn to theatro
Would coroma:	Drain on ward (achirata)	Interventional radiology	Return to theatre
would - seroma.	Drain on ward (aspirate)	drain	Return to theatre
Wound - haematoma:	Drain on ward (remove wound clips)	Requires antibiotics	Return to theatre
Incisional hernia:	<4cm in size	≥4 and <10cm in size	≥10cm in size
lleus:	<5 days	≥5 days, no IV feeding	IV feeding
Deep vein thrombosis:	Below the knee	Above the knee	Above the knee and extends into the vena cava
Pulmonary embolism:	Diagnosed radiologically, no effect on patient (except anticoagulant)	Endovascular intervention	Formal respiratory support / high care setting
Myocardial infarction:	Pharmacological treatment	Cath lab intervention (PCI)	ICU management
Delirium:	Occurs at night time only	Occurs at all hours	Psychiatric input required
Kidney failure:	IV fluid	Dialysis outside ICU	Dialysis in ICU
Pressure sore:	Grade 1 & 2	Grade 3/4	Surgical intervention
Permanent stroke:			Always severe
Return to theatre:			Always severe
Death:			Always severe
Anastomotic leak:	Antibiotics	Radiology intervention	Return to theatre
Anal/rectal stump	Antibiotics	Radiology intervention	Return to theatre
dehiscence:			
Mucotaneous	Superficial separation at	Involvement of dermis	Full MCJ separation
dehiscence:	the mucotaneous junction	layer leading to increase in	involving fat layer,
	(MCJ), either partial or	width or depth of	requiring primary wound
	circumferential	separation, partial or	dressing (stoma in
Channeller	Tichtening/neuroning.f		cavity/moat)
Stenosis:	the stome orifice no	functioning ribbon like	to dilate
	dilation required	stool	
Prolanse:	Variation in night and day	Persistent increase in	Persistent increase in
	length	length, functioning	length, non-functioning
Retraction:	Stoma partially retracted	Stoma mucosa below skin	Stoma below skin level
	below skin level but	level, managed with stoma	unable to manage with
	manageable with stoma	appliance/accessory	ostomy products
	appliance	,	
Ischaemia/necrosis:	Dark areas on stoma	Partial tissue death	Entire stoma cold and

			black (necrotic)
Peristomal skin	<25% affected area	≥25 and <50% affected	≥50% affected area
problems:		area	

#### 4.6 Primary and secondary outcomes

#### 4.6.1 Primary outcome

The primary outcome will be PSH incidence during follow-up after index surgery to form a stoma. An incident PSH is defined as:

- Symptoms of PSH (see 5.4), and
- Anatomical PSH, ascertained by independent reading of a CT scan (6)

Participants will describe their PSH symptoms using a custom-designed questionnaire, the "stoma questionnaire" [34]. Symptoms will be classified as green (asymptomatic), amber (mild/moderate symptoms) or red (severe symptoms). Cut-off points for these classifications will be defined on the basis of on-going data collection. We anticipate that severe symptoms may include recurrent problems with the stoma appliance, pain, or admission to hospital with obstruction. Mild/moderate symptoms are likely to be associated with discomfort and ill-fitting appliance issues managed by the patients themselves.

CT scans carried out in the course of a patient's usual NHS care will be assessed for all participants, with anatomical PSH being graded using the EHS classification (EHS class I, II, III or IV [24]). CT scans taken up to 6 months before or 3 months after the stoma questionnaire is completed will be valid for assessing anatomical PSH. The combination of symptomatic PSH and anatomical PSH confirmed by CT imaging will be our primary outcome. CT assessors will collect additional details from CTs (e.g. linear measurement of the PSH defect rather than just defect size >5cm vs ≤5cm), including a measure of the size of the PSH. The ESH criteria for classifying PSH as small or large will be reviewed on the basis of these additional data as the study progresses.

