#### 4.7 Justification of target sample size

The target sample size currently assumes an attrition rate of 10% at two years after index surgery. In practice, the power of the study will be increased by follow-up longer than two years for a proportion of participants and decreased by follow-up shorter than two years for a proportion (e.g. due to mortality, participants requesting to withdraw, or planned closures of loop ileostomies). These factors will be monitored as data accrues for the study, their consequences for the target sample size will be modelled and the target sample size revised if appropriate.

We have estimated the hazard ratio that the study will be able to detect for a range of scenarios. The incidence of PSH is unknown; we have considered incidences of 30% and 40% as plausible. Surgical methods of interest are used with varying frequencies and so we have considered the impact of a range of ratios for the use of technical variation when comparing one variation with another, i.e. ratios of 1:1, 1:2, 1:5, 1:10 and 1:20. The correlation of the exposure of interest with other covariates is also unknown and we considered the impact of a range of correlations (0, 0.3 and 0.5). The hazard ratios that can be detected from a study of 4000 participants at the 5% level (2-sided) are shown in **Table 3**. For simplicity, we have assumed a binary exposure variable. For multi-category exposures, we will assess the overall effect of the exposure; if we were to adjust the significance level from 5% to 2% to allow for comparisons between subcategories, the power reduces from 90% (80%) to 82% (68%).

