#### Figure 2: Data Collection Diagram

#### Footnotes:

- 1. SCNs will record the number of visits at 6 weeks, 6 months and 6 monthly thereafter; we also intend to obtain these data from the database used locally.
- 2. We intend to obtain data for all visits from the database used locally.
- 3. HES and ONS data should record all hospital activity but will only be extracted periodically.

	Time / frequency of data collection with respect to date of index surgery						
	Before	During	Up to discharge	6-weeks after	6-month after	12-month after	6-monthly to study end
Screening log	~						
Consent form	~						
Participant baseline details	~						
Surgical details		~					
Complications			~				
Index hospitalisation resource use		~	~				
SCN contacts with participants and hospital admissions				~	~	~	~
Exercise, support garment data				~	~	~	
EQ-5D-5L; SF-12	~			~	~	~	~
Wound questionnaire			~	~			
Community-based health care					~	~	~
Stoma questionnaire					~	~	~
Questionnaire about living with a stoma						~	
Request CT scans, taken as part of patient's usual care				~	~	~	~
Stoma care products issued				~	~	~	~
In-patient hospital episodes *					~	~	~
Out-patient hospital episodes *					~	~	~

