#### 8. Statistical analyses

#### 8.1 Plan of analysis

The data will be analysed according to the intention to implement a surgical step and will be reported in accordance with the principles of the CONSORT guidelines (but not items relating to randomization). A detailed statistical analysis plan will be prepared prior to locking the database. The primary outcome, time to PSH (defined as the time when PSH confirmed by imaging) and secondary time-to-event outcomes, will be analysed using survival methods. The models will take account of the hierarchical structure of the data; i.e. participants, nested within surgeons nested within centres. The hazards of key predictors will be estimated, with 95% confidence intervals, after adjusting for important procedure, patient and surgeon confounding factors.

Exploratory analyses will be used to inform the choice of survival distribution (e.g. Weibull). The factors included in the model, the modelling strategy and the approach to handling correlated covariates will be documented in the statistical analysis plan. Participants free from a PSH at final follow-up will be censored. Follow-up will also be censored if bowel continuity is restored, if participants have a redo stoma or die. These circumstances leading to censoring may be informative and sensitivity analyses (setting survival times to the longest observed times) will be undertaken to assess the potential impact of informative censoring. Secondary continuous outcomes will be analysed using a mixed regression models, again taking account of the hierarchical structure of the data and the repeated measurements over time. Binary outcomes (e.g. complications) will be analysed using

logistic regression. If the frequency of the outcomes allows, these models will also take account of the hierarchical structure of the data.

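### Time at risk for the primary outcome runs past the last stoma questionnaire, so with events dated at imaging, stomata closed early look falsely safer

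*Protocol*

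**What the plan says.** Section 4.6.1 makes an event depend on two things together: symptoms and an anatomical hernia on CT. For symptoms it names one source: "Participants will describe their PSH symptoms using a custom-designed questionnaire". A CT counts if taken from 6 months before to 3 months after that questionnaire.

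In the data collection schedule (Section 5.4, Table 4), the row "Stoma questionnaire" is ticked at 6 months, 12 months and 6-monthly to study end. It is not ticked at 6 weeks, and none is set for closure or redo.

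Section 8.1 defines the event time as the time of confirmation by imaging, and adds: "Follow-up will also be censored if bowel continuity is restored, if participants have a redo stoma or die". It accepts that this censoring may be informative and plans a sensitivity analysis that sets survival times to the longest observed.

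Section 4.7 treats shortened follow-up as a matter of power only, which is "decreased by follow-up shorter than two years for a proportion (e.g. due to mortality, participants requesting to withdraw, or planned closures of loop ileostomies").

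**The concern.** The end of time at risk and the last chance to observe an event are different dates. Whatever lies between them goes into the denominator, while a hernia that first becomes symptomatic there normally cannot enter the numerator.

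Two cases show it. A hernia symptomatic and visible on CT at month 4, with closure at month 5, gives 5 event-free months and no questionnaire. Onset at month 7 with closure at month 10 gives 10 event-free months, because the last questionnaire was at month 6.

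The gap is longest, relative to follow-up, for stomata closed early. Objective 2 compares end colostomy, loop colostomy and end ileostomy. If these are closed at different rates or times, an apparent difference in risk can arise with none in truth. Objective 1, the incidence, is pulled down. The bias review in Section 4.8 does not mention this.

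**Working it through.** **Benchmark: Table 3.** On its basis the protocol says: "The hazard ratios that can be detected from a study of 4000 participants at the 5% level (2-sided) are shown in" that table, and "we have considered incidences of 30% and 40% as plausible". The cells follow from HR = exp[(z_0.975 + z_power) / sqrt(N x incidence x (1 - R2) x p(1 - p))]. For a 1:1 ratio, R2 = 0 and 40% incidence, the root is sqrt(4000 x 0.4 x 0.25) = 20. This gives exp(3.242/20) = 1.18 at 90% power and exp(2.802/20) = 1.15 at 80%, as printed. All 60 cells reproduce within 0.005. The table runs from 1.15 to 1.86.

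**Simulation under no true difference.**
- Onset hazard, both groups: -ln(1 - 0.40)/24 = 0.0213 per month (40% at 2 years, the upper figure in Section 4.7).
- Death hazard: -ln(0.85)/24 = 0.0068 per month (15% at 2 years, Section 5.10).
- Questionnaires at 6, 12, 18 and 24 months (Table 4).
- An event counts only if the next questionnaire after onset comes before closure, death or 24 months.
- Assumptions: a CT is always available; imaging falls at random between onset and questionnaire; one group has 30%, 50% or 80% of stomata closed uniformly over months 3 to 12; the other has none closed.

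The crude rate ratio is events per person-month in the group with closures over that in the permanent group. Ranges span repeated runs.

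| Closed | True events ascertainable | Crude rate ratio | Cox HR, dated at imaging | 1 / Cox HR |
|---|---|---|---|---|
| 0% | 98% | 1 (reference) | 1 (reference) | 1 |
| 30% | 92% | 0.93 | 0.95-0.97 | 1.03-1.05 |
| 50% | 86% | 0.87 | 0.93 | 1.08 |
| 80% | 71% | 0.71-0.75 | 0.84-0.87 | 1.15-1.19 |

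The true value is 1.00 throughout. With 80% closed over months 3 to 18, the crude ratio is 0.79-0.80 and the Cox HR 0.89 (inverse 1.12). Table 3 is on the hazard-ratio scale, so the last column is the one to compare with it. Only the 80% row reaches its smallest cell, 1.15.

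**What the size depends on.** These checks close every stoma in one group, an extreme case.
- Closure within months 3 to 9 or 3 to 12, CT before the questionnaire: Cox HR 0.61-0.68.
- The same closure, with CTs up to 3 months after the questionnaire also used: Cox 0.71-0.80, Weibull 0.76-0.89.
- Closure at 6 to 18 or 12 to 24 months, with those later CTs: Cox 0.91-0.97, Weibull 1.02-1.05, so near null.
- Events dated at the questionnaire instead of at imaging: Cox 0.95-1.09 (1.00-1.01 in the scenarios of the table), but a right-censored Weibull 0.99-1.51, so it can err the other way.

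**The planned sensitivity analysis.** Setting survival times to the longest observed adds still more event-free time to closed stomata. In the all-closed case the Cox HR becomes 0.11-0.19 for early closure and 0.44-0.74 for later closure.

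**The remedy tested.** Ending time at risk for non-events at the last completed questionnaire gives ratios of 0.98-1.05 in every scenario. An interval-censored Weibull model on questionnaire dates gives 0.98-1.03.

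**The case against.** A reader might infer that the comparison is biased whichever survival method is used. It is not. The lost events are lost under any method, but a Cox model with events dated at the questionnaire is about unbiased, and so is an interval-censored model. Section 8.1 leaves the survival distribution and modelling strategy to the analysis plan. What stands is that Section 8.1 itself fixes the imaging date as the event time and closure, redo or death as the censoring date, and that combination produces the bias.

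A reader might also take the crude ratios as the size and conclude that the bias rivals the effects the study is powered for. The protocol plans hazard models, where the bias is about half as large, and most assumed closure patterns stay below every cell of Table 3.

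The affected group is uncertain. The only planned closures the protocol names are of loop ileostomies, which Objective 1 leaves out and Objective 2 does not list. For the types compared, no closure shares are given, so the contrast at issue is chiefly loop colostomy against end stomata. Comparisons of surgical steps are affected only where a step goes with closure after the planned adjustment; the documents do not show that any does.

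Finally, it is too strong to say that such a hernia can never count. The protocol does not say that questionnaires stop at closure, so a CT at month 4 might qualify through a month-6 questionnaire completed after closure. After month 6, a CT following an already positive questionnaire can also yield an event before closure. The point therefore concerns new symptom onset after the last questionnaire.

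**Conclusion.** The concern holds in limited form. The mechanism follows from rules the protocol states, and with events dated at imaging its direction for early closure is towards false safety. In permanent stomata only about 2% of true events are lost, so the effect on Objective 1 depends on how many stomata are closed. For Objective 2, the spurious Cox hazard ratio is about 0.95-0.97, 0.93 and 0.84-0.87 for 30%, 50% and 80% closure over months 3 to 12.

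These figures rest on assumed closure shares and timing, a constant hazard and a CT always available. Later closure combined with CTs after the questionnaire brings the bias near null. The sensitivity analysis in Section 8.1 does not address the problem and pushes in the same direction. The change is worth making because it is cheap and removes the bias under every pattern tried.

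**What to change.** In Section 8.1, end time at risk for participants without an event at their last completed stoma questionnaire while the index stoma is in place, not at the date of closure, redo or death. Alternatively, fit an interval-censored model on questionnaire dates.

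The cost is wording and some person-time. Participants closed before 6 months contribute nothing to the primary analysis. Under the closures assumed above, deaths aside, that is the share closed x 3/9: 10%, 17% or 27% of the stoma type. Symptomatic hernias in those stomata stay unknown, and the report should say so.

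A 6-week questionnaire is not worth adding: it moves the crude ratios only from 0.93 to 0.94, 0.87 to 0.89 and 0.72 to 0.76. A questionnaire at closure would recover events otherwise lost, but is optional and should be used only with interval-censored analysis. On its own it moves the Cox HR above 1 (1.03-1.14 dated at imaging, up to 1.35 dated at the questionnaire), because closed stomata then get an extra assessment.

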#### 4.6.2 Secondary outcome measures

Secondary outcomes include:

- 1. Intensive care unit (ICU) stay (days) during admission for index surgery
- 2. Hospital stay (days) during admission for index surgery and associated costs
- 3. Surgical site infection during admission for index surgery and 30 days afterwards
- 4. Other complications, documented using the Clavien Dindo classification [35] and the Comprehensive Complication Index [36, 37]
- 5. Questionnaire to assess symptoms of PSH (developed in Phase A; REC 16/EM/0155)
- 6. Generic health status (EQ-5D-5L, SF12 [38, 39]), which will be combined with survival to estimate QALYs
- 7. Appointments with SCNs, stoma care products used and associated costs
- 8. PSH repair (procedure codes for stoma formation in HES, information from SCNs) and associated hospital costs
- 9. Estimated cost of hospital care during follow up and primary care, social care and societal costs associated with stoma.

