## 2.2.2 The economic burden of PSH

The economic impact of PSH on the NHS is poorly understood because accurate data regarding stomata are difficult and expensive to extract [7]. However, it has been reported that patients with symptomatic stoma are more likely to have increased rates of consultation with community healthcare teams [8], and increased direct costs related to stoma bags and associated products such as belts, adhesives, sprays, wipes and barrier creams. The cost of stoma bags and associated products was over £228m in 2012 in England alone [9] and costs have risen over 30% in the past 5 years. Skin irritation, one of the commonest problems associated with PSH, is estimated to cost an additional 50 Euro per patient over a 7 week treatment period [10]. The cost of bags and accessories for a patient managing a stoma effectively varies between £780 and £1800 per year; this sum can rise to £6000 per year when a PSH is present [11]. Furthermore, none of the estimated costs incorporate the expense and / or time of the approximately 600 stoma care nurses (SCNs) in the UK.

Some PSH may be repaired surgically and emergency surgical intervention is indicated in some circumstances, e.g. if a PSH causes bowel obstruction. The precise number of PSH repair procedures performed annually in the NHS is currently unknown due to variation in coding. PSH repair performed as elective surgery may be recorded alone or as part of a more complex incisional hernia repair; emergency repair may be recorded as part of a laparotomy. Regardless of coding, PSH repair is associated with significant costs including: the patient's in-hospital stay (including in critical care units), theatre time, intra-operative equipment used and the cost of mesh implants. Unfortunately, complications following PSH repair surgery are common and the hernia recurrence rate is high, leading to further interventions [12-14].

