## Table 4:Timing and frequency of collection of data items

Footnotes:

\*In-patient and out-patient hospital episodes will be extracted from HES data, which will be requested periodically throughout the study.

Data collection will include the following elements:

- (a) A screening log of patients undergoing elective surgery to form a stoma. This log will be maintained by centres but data from the log will only be entered for eligible patients who consent to take part in the study (i.e. participants).
- (b) Confirmation of patient's eligibility against all eligibility criteria, written informed consent and patient's contact preferences (see below).
- (c) Baseline data characterising participants before surgery will be collected by the SCNs and obtained retrospectively from a HES data extract. Data from these sources will include any relevant diseases and comorbidities the participant may have and their current health status.
- (d) Surgery details will be collected by the surgical team in theatre and entered into an online database. These details will describe how the stoma is formed.
- (e) Details of a participant's recovery after surgery will be collected at discharge by the SCNs and obtained retrospectively from a HES data extract. These details will describe the patients post-operative stay including surgical or medical complications.
- (f) All follow up contacts between a participant and a SCN will be recorded by the SCNs; we also intend to obtain these details from local NHS stoma care databases used by hospitals when available.
- (g) Participants will be asked to complete health questionnaires, i.e. the EQ-5D-5L and SF-12, a purpose-designed questionnaire about stoma symptoms developed in Phase A [34], a questionnaire about how the participant is adapting to living with a stoma [43] and brief questions about primary care, social care and other resource use related to the stoma. Participants will be able to choose to receive the questionnaires by post or to complete them via an online secure website. Subject to their consent, we may also issue reminders to participants about completing questionnaires by text messaging.

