## 8.4 Economic analysis

The economic analysis aims to estimate the cost effectiveness of commonly used mesh types (e.g. biologic, synthetic) versus no prophylactic mesh in preventing PSH and improving health related quality of life. The intervention groups to be compared will be finalised after recruitment so that they consist of clinically and economically similar interventions in common clinical use. A detailed health economics analysis plan will be prepared prior to locking the database [44].

The primary economic evaluation will be a cost-utility analysis from the NHS perspectives. A secondary analysis will be from a broader perspective (social care, personal costs). We will conduct the primary evaluation at 2 years after index surgery. We estimate that 30% to 40% of participants will have developed a PSH, allowing major differences in the post-surgical cost between the options for different types of mesh to be detected. If differences in the incidence of PSH, quality of life or stoma care costs over 2-years indicate that interpretations of cost-effectiveness might be sensitive to the duration of follow up (e.g. expensive interventions might become cost-effective in the longer term) we will also carry out an evaluation over a lifetime horizon making assumptions about the trajectory of PSH incidence, PSH repair, on-going stoma care costs, QALYs and survival.

NHS costs include those associated with (i) the operation (ii) the post-operative in-patient stay and (iii) stoma care and PSH repair during follow-up. As the insertion of mesh accounts for only a small fraction (5-10 minutes) of the whole procedure, the predominant differential cost of using mesh during the index procedure is the cost of the implant itself. We will estimate the unit cost of mesh based on the purchase price at a range of hospitals participating in the study. We will use NHS reference costs (including excess bed day costs) to estimate the cost of the index hospitalisation, based on length of stay. Subsequent stoma care contacts and products, and stoma-related primary and social care use will be costed using nationally published sources. Information on subsequent in-patient (e.g. PSH repair) and out-patient hospital care from HES will costed using NHS reference costs [45-47].

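### Secondary outcome 8 names stoma-formation codes as the HES source for PSH repair, which does not match the protocol's own account of how repairs are recorded

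*Protocol*

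**What the plan says.** Section 4.6.2 lists as secondary outcome 8 "PSH repair (procedure codes for stoma formation in HES, information from SCNs", together with the hospital costs of those repairs. Two sources are named, a HES code set and SCN information. The code set is described by the operation that creates a stoma.

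Section 2.2.2 describes how repairs reach the record. On elective surgery: "PSH repair performed as elective surgery may be recorded alone or as part of a more complex incisional hernia repair". On emergencies: "emergency repair may be recorded as part of a laparotomy". It also concedes the general difficulty: "The precise number of PSH repair procedures performed annually in the NHS is currently unknown due to variation in coding".

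Section 8.1 treats a later stoma as an event of its own: "Follow-up will also be censored if bowel continuity is restored, if participants have a redo stoma or die". Section 8.4 relies on HES for costing later hospital care, with repair as the example: "Information on subsequent in-patient (e.g. PSH repair) and out-patient hospital care from HES".

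No section names hernia-repair codes or corrects the wording of outcome 8.

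**The concern.** An outcome taken from routine data is only as good as the codes that define it. Here the stated codes describe a different procedure from the outcome. Two errors follow, in opposite directions. A repair that leaves the existing stoma in place has no reason to carry a stoma-formation code, so HES would not identify it. A participant who later has a new stoma for a reason unrelated to hernia would be counted as having had a repair.

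Outcome 8 reports both the repairs and the hospital cost attached to them, so both are exposed. The footnotes to Figure 2 present HES as the source that should hold all hospital activity. That makes the choice of codes more important.

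**Working it through.** The documents give no repair rate, code list or coding accuracy, so there is no figure to reproduce. The check sets the stated rule against the events that the protocol itself describes.

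| Event after the index admission | Where described | Stoma-formation code expected? | PSH repair? |
|---|---|---|---|
| Elective repair recorded alone | 2.2.2 | No | Yes |
| Elective repair within an incisional hernia repair | 2.2.2 | Not unless a new stoma is also made | Yes |
| Emergency repair within a laparotomy | 2.2.2 | Not unless a new stoma is also made | Yes |
| Emergency surgery for PSH that includes revising the stoma | Phase A protocol, section 2 | Possibly | Depends on what was done |
| Redo stoma for a reason other than PSH | 8.1 (redo stoma as a censoring event, no reason given) | Yes | No |

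The rule does not correspond to any of the three recording routes in section 2.2.2, and it does pick up the last row.

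To see what the size would depend on, let N be the true number of repairs, s the share of them that carry a stoma-formation code, and R the number of redo stomas made for other reasons. Then:

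- HES count = s × N + R
- Error in the HES count = (s × N + R) − N = R − (1 − s) × N

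The documents give no value for N, s or R. The share s could lie anywhere from 0 (no repair found through HES) to 1 (all found). Neither the size nor the net sign of the error can therefore be stated. The two parts could offset each other in the total and still misclassify individual participants. SCN reports would reduce the (1 − s) × N term by an unknown amount. If they are only added to the HES count, they do not remove R.

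The data for a correct rule are already planned. Section 5.4 provides for periodic linked HES extracts of in-patient episodes, and Table 4 schedules SCN recording of hospital admissions at 6 weeks, 6 months, 12 months and every 6 months to study end. The fault is in the description of the codes and not in data availability.

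**The case against.** The strongest reply is that the bracket only names sources, and that the working code list belongs in the statistical analysis plan or the health economics analysis plan, both promised before database lock. That disposes of any complaint that a code list or an index-date rule is missing. It does not dispose of the words that are there, because a later plan that followed them would take over the wrong code set.

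Three further points stand and limit the claim:

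- SCN information is a named second source with scheduled recording of admissions, and section 5.4 adds local stoma care databases. Some repairs would be recovered.
- It would be too strong to say that the rule misses repairs in general. Some operations for PSH revise the stoma and could carry a stoma code, and section 2.2.2 says how repairs may be recorded without claiming to be exhaustive.
- Section 2.2.2 also warns of variable coding, so a replacement rule that leans entirely on diagnosis codes could lose repairs in its turn.

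Two stronger readings are tempting, and the documents do not support them. A reader might infer that every participant would be flagged, since all have a stoma formed at index and the details of recovery "will be collected at discharge by the SCNs and obtained retrospectively from a HES data extract". But those index data serve to describe recovery and complications, section 8.4 speaks of subsequent in-patient care, Table 4 places the HES in-patient item from 6 months onward, and patients with a previous stoma are excluded. Counting the index operation as a repair is an unlikely reading.

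A reader might also infer that the cost-effectiveness comparison of mesh is biased. Section 8.4 appears to cost HES in-patient care whether or not it is labelled as PSH repair, outcome 9 covers hospital costs during follow-up separately, and QALYs come from EQ-5D-5L and survival. Section 8.4 does list PSH repair as a cost component, and a lifetime extrapolation, if done, would make assumptions about repair. Some ambiguity remains, but a distorted cost-utility result is not demonstrated.

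**Conclusion.** The point holds in a limited form. Outcome 8 states an identification rule that disagrees with the protocol's own description of the coding. The HES component would miss repairs done without a new stoma and would count redo stomas formed for other reasons, which section 8.1 handles as a separate censoring event. The number affected and the net direction cannot be derived from the documents.

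The quantities exposed are the count of PSH repairs and the cost attributed to them in one of nine secondary outcomes. The primary outcome and the sample size are untouched. The conclusion assumes that the bracket would be applied as worded, and that section 2.2.2 fairly describes how repairs are usually recorded. The wording should be corrected before the code list is drawn up.

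**What to change.** Replace the bracket in outcome 8 so that PSH repair is identified from HES episodes after the index admission by:

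1. procedure codes for parastomal and incisional hernia repair;
2. procedure codes for stoma revision or re-siting;
3. laparotomy episodes with a parastomal hernia diagnosis;

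combined with SCN reports. A stoma-formation code after index should only flag a possible re-siting or redo stoma. It should count as a PSH repair when either a PSH diagnosis or an SCN report supports it. Accepting either is deliberate: requiring a diagnosis code in the same episode would depend too heavily on coding that section 2.2.2 calls variable.

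The cost is a revised code list applied to extracts already planned, and some reliance on diagnosis coding. No new data or patient contact is needed.
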